7.5. Adjustments for Multiple Comparisons

Only one statistical analysis will be run for primary endpoint assessment (single testing), after all subjects completed the study. Therefore, there is no need for adjustment in the study.

7.6. Demographic and Other Baseline Characteristics

Demographics characteristics, medical/surgical histories and other risk-factors for incisional hernia occurrence will be summarized using descriptive statistics, based on Performance Analysis Set, Safety AS and per protocol AS.

7.7. Treatment Characteristics

Indication for abdominal surgery, operative data (such as ASA class, anesthesia and surgery duration), surgical technique for abdominal wall surgery as well as implanted mesh characteristics will be described. Some subgroup analyses may be run according to indication for surgery and surgical data, for efficacy and safety evaluation.

7.8. Interim Analyses

After half of the subjects completed the 1-year follow-up timepoint, an interim analysis (secondary endpoints assessment only) will be conducted for regulatory purpose.

7.9. Evaluation of Objectives

Primary Objective and Endpoint

The primary objective of this investigation is to confirm the efficacy of ProGrip™ Self-gripping Polyester Mesh to reduce the incidence of incisional hernia within 24 months post-operatively in subjects undergoing procedure with midline laparotomies.

The primary endpoint is the incisional hernia rate within 24 months of midline laparotomy assessed by CT-scan and physical examination including hernia clinical examination.

Statistical analysis of primary endpoint will be comparative. Binomial one-way test will be used to compare the observed ProGrip™ Self- gripping Polyester Mesh incisional hernia incidence rate to the 20% theoretical incidence rate (from no prevention population), using a two- sided alpha-level of 5%.

Primary endpoint will be measured using Performance Analysis Set; a confirmatory analysis of primary endpoint will be run using Per Protocol Analysis Set.

Secondary objective and endpoints

The secondary objective of this investigation is to confirm the safety of ProGrip™ Self-gripping Polyester Mesh through the occurrence of adverse device effects or procedure related adverse events following the use of ProGrip™ Self-gripping Polyester Mesh in subjects undergoing procedures with midline laparotomies.

To confirm the safety of ProGrip™ Self-gripping Polyester Mesh through the occurrence of adverse device effects or procedure related adverse events following the use of ProGrip™ Self-gripping Polyester Mesh in subjects undergoing procedures with midline laparotomies.

The following secondary endpoints will be assessed:

- Adverse event (AE) incidence reported by number, severity, seriousness and relationship to the procedure and device from the surgery to the 24-month visit: AE incidence will be measured on Safety Analysis Set.
- Time to incisional hernia occurrence: will be measured using Kaplan Meier estimates, and based on SAS, and PPAS.
- Post-operative pain at the site of surgery: will be measured on SAS and PPAS, at each postoperative timepoint: Day0 (after surgery), Day1, Day8, Day30, Month12 and Month24.
- Quality of life: will be measured on all, PAS, SAS, and PPAS, using Club Hernie QOL questionnaire, combining qualitative and quantitative data, at Month1, Month12 and Month24.
- Patient satisfaction: at 12 then 24 months, measured on PAS, PPAS and SAS
- Surgeon satisfaction, measured on PAS, SAS, and PPAS

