# 15. Statistical Design and Methods

## 15.1 General Aspects of Analysis

For each of the objectives the available data will be summarized and missing data will be discussed. The main analysis of the study objectives will be based on available data and missing data will not be imputed unless otherwise noted in the statistical analysis plan. All practical monitoring and follow-up steps will be taken to ensure complete and accurate data collection. Deviations to the statistical analysis plan (SAP) will be reported per section 11.12 (Deviation Handling).

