Informed consent	X ²								
Pregnancy Test	X								
Subject demographics	X								
Relevant prior medical/surgical history	X								
Surgical Data									
Date of surgery		X							
Procedure indication		X							
Surgical technique for laparotomy closure		X							
Mesh reference and lot number		X							
Type of fixation		X							
Operative time		X							

Procedure/Assessment	Screening (Day -30 to 0)	Operative (Day 0)	Post-operative course (Day 0) Follow up	Post-operative course (Day 1) Follow up	Discharge Assessment	Post-operative course (Day 8, +/-2days) Follow Up	1 Month (Day 30, +/-1week) Follow-up	12 Months (-1/+4 weeks) Follow-up	24 Months (-1/+4 weeks) Follow-up
	Can be combined								
Mesh positioning and time		X							
Peri-operative events including adverse device effects or procedure related adverse events		X							
Surgeon satisfaction		X							
Post-operative data									
VAS pain assessment			X	X		X	X	X	X
Post-operative adverse events				X	X		X	X	X
Date of discharge					X				
Length of Hospital stay					X				
Physical exam including hernia clinical examination							X	X	X
Abdominal CT Scan								X	X
Quality of Life Questionnaire							X	X	X
Patient Satisfaction								X	X
1-month prior phone call including self-assessments								X	X
Study Exit									X
1. If Screening and Surgery occur on different days, these procedures should occur during Screening and be reconfirmed on the day of surgery. 2. No study procedures will be performed until informed consent form has been completed. Subject should be re-consented if date of original consent is greater than 30 days.									

6. Determination of Sample Size

Sample size is determined based on primary performance endpoint, assuming the superiority of ProGrip™ Self-gripping Polyester Mesh use to prevent incisional hernia vs no prevention of incisional hernia within 2-years following a midline laparotomy procedure.

The literature review showed an incisional hernia rate after midline laparotomies around 20% (9-16). Using a power ($1-\beta$) of 80% and a 5% error type I (two-sided), and considering a hypothetical incisional hernia rate of 10% for subjects with ProGrip™ Self-gripping Polyester Mesh, vs a theoretical hypothetical incisional hernia rate of 20% for subjects without any prevention following a midline laparotomy procedure, N= 108 evaluable subjects are required.

Assuming an attrition rate of 20% at 2-years, N=135 subjects will need to be enrolled.

7. Statistical Methods

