7.1.3. Analysis Sets

Statistical analysis will be performed on:

- Performance Analysis Set (PAS): includes all enrolled subjects excluding subjects who became pregnant during the follow-up, or subjects who undergo unscheduled abdominal surgery during study follow-up, which may increase the risk and cause of incisional hernia occurrence*.

*Subject follow-up data, starting from the event's occurrence, will be excluded/remove from the performance analysis.

- Per Protocol Analysis Set (PPAS): a subset of PAS excluding subjects with protocol violation and major protocol deviation(s) that may impact the primary endpoint assessment. More precisely, reason for exclusion may include but is not limited to:
 - Patient wrongly included (*i.e.* patient was enrolled but does not meet all the eligibility criteria).
 - Failure to obtain informed consent.
 - Deviation resulting from device use outside the recommended use in the IFU.
 - Patient who receives the incorrect device or device is misused
- Safety Analysis Set: includes all enrolled subjects.

Performance analyses will be run on Performance Analysis Set (PAS) and on Per Protocol Analysis Set (PPAS) as confirmatory analysis.

Safety analyses will be run on Safety Analysis set (SAS) and on Per Protocol Analysis Set (PPAS), as confirmatory analysis.

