7.2. General Methodology

At the exception of Primary endpoint analysis which will be comparative (see details in section 7.9 Evaluation of Objectives), statistical analysis will be mainly descriptive.

Some subgroup comparative analyses may be run in addition to primary and secondary endpoints, to assess impact of demographic characteristics, risk-factors, indication for surgery, operative data and surgical technique applied.

- Qualitative variables will be described by their absolute and relative (%) frequencies of each class or value, and by two-tailed 95% confidence intervals.

- Quantitative variables will be described by their mean, standard deviation (SD), extreme values (minimum and maximum values), and number of missing data and by two-tailed 95% confidence intervals.

Continuous variables will be summarized using counts, means, and standard deviations, medians, minimum, maximum and 95% confidence Interval (CI).

Categorical variables will be summarized using absolute and relative (%) frequencies of each class or value, and by two-tailed 95% confidence intervals.

Statistical analysis will be implemented on overall subjects, using 1 analysis sets, as described previously (Section 7.1.3).

Comparative subgroup analyses will be performed using:

- Pearson Chi-square test or Exact test will be used (as appropriate) for categorical data
- Student t-test or Wilcoxon rank sum test will be used if assumptions or t-test are not verified for continuous data.

Primary and secondary endpoints analyses are described in detail in section 7.9 *Evaluation of objectives*.

Statistical analyses will be run using SAS® v9.4 system, and statistical outputs will be provided in text files.

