7.4. Handling of Missing, Unused, and Spurious Data and Dropouts

No data imputation will be performed for missing data unless otherwise noted in statistical analysis plan. All practical monitoring and follow-up steps will be taken to ensure complete and accurate data collection.

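### The 24-month AE incidence is planned as a plain percentage of the Safety Analysis Set with no allowance for incomplete follow-up, so late adverse events are likely to be understated

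*SAP*

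**What the plan says.** - **Window and set.** SAP 7.9 lists AE incidence as a secondary endpoint "from the surgery to the 24-month visit" and states that "AE incidence will be measured on Safety Analysis Set". SAP 7.1.3 defines the set: "Safety Analysis Set: includes all enrolled subjects".
- **Summary.** SAP 7.2 gives the general rule: "Categorical variables will be summarized using absolute and relative (%) frequencies of each class or value, and by two-tailed 95% confidence intervals". SAP 7.10 adds listings and MedDRA tabulation, but no person-time, interval or time-to-event summary of AEs.
- **Incomplete follow-up.** SAP 7.4: "No data imputation will be performed for missing data unless otherwise noted in statistical analysis plan". Protocol 15.1: "The main analysis of the study objectives will be based on available data". Neither states the denominator for AE percentages.
- **Expected attrition.** SAP 6: "Assuming an attrition rate of 20% at 2-years, N=135 subjects will need to be enrolled".
- **Contrast within SAP 7.9.** Time to incisional hernia, in the same list of secondary endpoints, is to be estimated by Kaplan-Meier.
- **Exit rules.** Protocol 11.13.1 ends data collection at exit and keeps what was recorded before it. Under 11.13.5 nobody is classed as lost until the study ends. Under 11.13.6 a subject exits 30 days after mesh removal.

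**The concern.** A percentage with a fixed denominator estimates 24-month risk only if everyone in that denominator was observed for 24 months, or until the event or death. If a subject leaves at month 10 without an AE and stays in the denominator, the calculation treats months 10 to 24 as observed and clean. The SAP deals with this for hernia but not for AEs.

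The effect falls on late events. Early surgical complications occur while nearly everyone is still under observation. After Day 30 the only scheduled visits are at 12 and 24 months (Protocol Table 2), so missing the last one can remove up to a year of scheduled AE ascertainment. The device is a permanent implant and confirming its safety is the secondary objective, so the late period matters most to a reader of the report.

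**Working it through.** **1. The plan's own figures.** One-sample comparison of 10% with 20%, two-sided 5%, power 80% (SAP 6), normal approximation:

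n = [(1.960 × √(0.2 × 0.8) + 0.8416 × √(0.1 × 0.9)) / 0.1]² = [(0.7840 + 0.2525) / 0.1]² = 107.4, rounded up to 108.

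108 / (1 − 0.20) = 135. Both stated figures reproduce. The plan therefore allows for 135 − 108 = 27 subjects not evaluable for hernia at 2 years. It states no expected AE rate, so there is no AE figure to reproduce.

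**2. Effect on a crude AE percentage.** Let G(t) be the share of subjects still under AE observation at month t. If loss is unrelated to AE risk, then

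expected crude proportion = true 24-month risk × average of G(t) over the times at which events occur.

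Assumptions, none of them given in the documents: AE follow-up loss reaches 20% by month 24, and events are evenly spread within each window below. With uniform loss over 24 months, G(t) = 1 − 0.2 × t/24, so the ratios of crude to true risk are:

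- First month: 1 − 0.2 × 0.5/24 = 0.996
- Months 0-24: 1 − 0.2 × 12/24 = 0.90
- Months 12-24: 1 − 0.2 × 18/24 = 0.85
- Found only at month 24: 1 − 0.2 = 0.80

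**3. Sensitivity to when loss occurs.**

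| Events occur in | Loss uniform over 24 months | All loss uniform over the first 12 months |
|---|---|---|
| First month | 0.996 | 0.992 |
| Months 0-24 | 0.90 | 0.85 |
| Months 12-24 | 0.85 | 0.80 |
| 24-month visit only | 0.80 | 0.80 |

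A constant dropout hazard in place of uniform loss gives almost the same values (0.995, 0.896, 0.846, 0.80). If all loss falls after the events, the ratio is 1.00. If all loss came straight after surgery, it would be 0.80 for every type of event. With 20% loss unrelated to risk, the ratio cannot fall below 0.80.

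**4. In percentage points (uniform loss).**

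| True 24-month risk | Events over 0-24 months | Events in months 12-24 | 24-month visit only |
|---|---|---|---|
| 2% | 1.8% | 1.7% | 1.6% |
| 5% | 4.5% | 4.25% | 4.0% |
| 10% | 9.0% | 8.5% | 8.0% |

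**5. Effect of the denominator on reported figures.** Eleven subjects with an event are 8.1% of 135 (exact 95% CI 4.1 to 14.1) and 10.2% of 108 (5.2 to 17.5). With no events, the exact upper limit is 2.7% on 135 and 3.4% on 108. Dividing by 108 is not the remedy, because subjects lost part-way contribute real observation before they leave. The two figures show only how far the choice can move the result.

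**The case against.** The case against is substantial, and several parts of it stand.

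- **The denominator is inferred.** A reader might infer that the plan rules lost subjects to be event-free. It does not: the SAP names an analysis set and a generic percentage rule, and the protocol's available-data wording leaves room for another denominator. But if the denominator is open, the SAP still needs to state it.
- **The 20% is not an AE figure.** A reader might infer that 27 of 135 subjects will be gone for safety purposes. The figure inflates N for the hernia endpoint, which needs CT and examination. A subject without a CT can still report AEs. Late visits are analysed (Protocol 11.3), subjects are phoned before the 12- and 24-month visits (11.7.6, 11.7.7), and missed visits trigger repeated calls and a letter (11.13.5). Actual AE loss may be smaller.
- **Not every AE is affected.** A reader might apply a 10-20% understatement to the whole AE table. The early events that the protocol names, such as infection, hematoma and seroma, are barely touched unless loss comes almost at once after surgery.
- **Mesh removal is not a missed event.** Removal precedes the exit that it triggers. Unresolved related AEs are also followed for up to 30 days after an early exit (13.3). Only new events after observation stops are missed.
- **Deaths belong in the denominator.** Subjects who die cannot have later AEs, so that part of attrition causes no bias in a cumulative incidence.
- **No decision turns on it.** The AE analysis is descriptive, without a threshold. A shift of 1 to 2 points on an assumed 10% lies well inside the interval for 11 of 135. SAP 7.1.1 also tabulates disposition by follow-up, so incomplete follow-up will be visible, though it is not linked to the AE rates.

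These points limit the size and wording of the concern. They do not supply an analysis that allows for incomplete follow-up.

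**Conclusion.** The point holds as a gap in the planned AE analysis: a 24-month risk is to be summarised by a percentage that ignores incomplete follow-up, in a study that plans for attrition and handles censoring for hernia. On the natural reading, late AEs are understated. With AE loss equal to the 20% assumed for hernia evaluability, unrelated to AE risk and uniform over 24 months, the relative understatement is under 1% for first-month events, about 10% for events over 24 months, about 15% for months 12-24, and at most 20%, reached for events found only at the 24-month visit. Deaths, or loss after the events, reduce it. If loss depends on AE risk, these figures no longer bound the effect.

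The documents do not support saying that the SAP fixes this denominator, that 20% of subjects will be lost to AE follow-up, or that all AE rates are too low by 10-20%. This is an inexpensive improvement to safety reporting and does not affect the primary test.

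**What to change.** Amend SAP 7.9 and 7.10 as follows.

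1. Keep the crude AE table and state its denominator.
2. Add AE incidence by interval (0-30 days, 30 days-12 months, 12-24 months), each with the number of subjects under observation.
3. For device-related AEs and for SAEs, add the 24-month cumulative incidence of first event with a 95% CI, treating death as a competing event. Censor at the last AE assessment, not at the date when loss is declared, because Protocol 11.13.5 defers that declaration to the end of the study.
4. State that exit after mesh removal (Protocol 11.13.6) may be informative censoring, and report how many subjects left for that reason.
5. Do not rely on a single rate per 100 subject-years. Surgical AEs cluster early, so a constant-rate summary would average over very different periods.

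The cost is a few extra tables. AE dates are already collected (Protocol 13.5), but the date of the last AE assessment must be derived for each subject. Late AE figures will probably look slightly less favourable, and their intervals wider.

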## 10. Selection of Subjects

### 10.1. Study Population

At least 135 subjects undergoing midline laparotomy may be enrolled in up to 12 sites in France using the embedded registry data of Club Hernie. Each site will be allowed to enroll between 1 and 25 subjects. To reduce bias, enrollment will not exceed 25 subjects per site. No randomization, or blinding will take place during the study.

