## **11.6 Operative Day (D0)**

The following information is required to be collected on the operative day:

- Date of surgery
- Indication of the procedure
- Surgical technique for laparotomy closure (closure technique and type of suture)
- Mesh reference (TMP1509G, TMP1515G, TMP2015G, TMP3015G, TMP1008G, TMP2008G, TMP3008G, TMP4008G) and lot number
- Type of fixation
- Operative time (from incision to closure, skin to skin),
- Mesh positioning and time
- Peri-operative events including adverse device effects or procedure related adverse events
- Surgeon satisfaction (Club Hernie questionnaire regarding surgeon satisfaction of mesh handling, mesh manipulability, ease of use)

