7.3. Center Pooling

The study will be conducted in a minimum of 6 and maximum of 10 investigational sites. Baseline and surgical data will be summarized for overall subjects and for each site separately, to confirm homogeneity of subject's characteristics between sites.

Enrollment will not exceed 25 subjects per site, which avoid imbalance between sites.

Primary and secondary endpoint analysis will be run on overall subjects and sites.

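### The planned 95% CI for surgeon satisfaction makes no allowance for surgeons who rate repeatedly, so it is too narrow if ratings correlate within surgeon, by an amount the documents do not fix

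*SAP*

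**What the plan says.** Protocol 11.6 lists among the data required on the operative day: "Surgeon satisfaction (Club Hernie questionnaire regarding surgeon satisfaction of mesh handling, mesh manipulability, ease of use". The schedule of events (Protocol 11.2, Table 2) places the item in the operative-day column. This means one rating per implanted subject, given by the surgeon.

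SAP 7.9 plans the endpoint as "Surgeon satisfaction, measured on PAS, SAS, and PPAS". All three are sets of subjects; for example, SAP 7.1.3 has "Safety Analysis Set: includes all enrolled subjects".

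SAP 7.9 names no interval for this endpoint. The interval comes from the general rule in SAP 7.2. For categorical data: "Qualitative variables will be described by their absolute and relative (%) frequencies of each class or value, and by two-tailed 95% confidence intervals". For continuous data the rule is a mean, SD, median, range and 95% CI. SAP 7.3 adds: "Primary and secondary endpoint analysis will be run on overall subjects and sites".

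On the number of raters, Protocol 10.1 says "Each site will be allowed to enroll between 1 and 25 subjects", at up to 12 sites. SAP 7.3 instead says "The study will be conducted in a minimum of 6 and maximum of 10 investigational sites". Protocol 9.1 expects each site to have one or more qualified investigators. Neither document states how many surgeons will implant, mentions clustering by surgeon or site, or plans a per-surgeon summary.

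**The concern.** Handling, manipulability and ease of use are personal judgements, and Protocol 8.5 shows that investigators start with different experience of the mesh. Ratings from one surgeon are therefore likely to resemble each other more than ratings from different surgeons. A standard CI over about 135 subjects counts each rating as a separate piece of information. With positive within-surgeon correlation it overstates precision.

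What is at stake is the reported precision of one listed secondary endpoint. No test, threshold or decision rests on it. Two features make a correction before analysis worthwhile. The interim analysis in SAP 7.8 is for regulatory purposes and covers secondary endpoints only, so the interval may be reported early. And SAP section 8 gives secondary endpoints only the original programmer's own visual check, which is unlikely to catch a missing cluster term.

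**Working it through.** **The plan's own figure.** The documents give no CI width for surgeon satisfaction. The only related figure is the subject count, and it reproduces: n = [(1.960·√(0.2·0.8) + 0.842·√(0.1·0.9)) / 0.10]² = 107.4, rounded up to 108; 108/0.80 = 135. The 20% attrition concerns 2-year follow-up and does not touch a day-0 rating, so about 135 ratings is the right count on the Safety Analysis Set.

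**Ratings per site.** 135/12 = 11.25 with the protocol's maximum number of sites; 135/6 = 22.5 with the SAP 7.3 minimum.

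**Assumptions, not in the documents.** The item is yes/no with 80% satisfied. There are 12 surgeons (one per site at the maximum site count) or, as a favourable case, 40. ICC is 0.01 to 0.3. Ratings are spread evenly over surgeons.

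**Unadjusted half-width.** 1.96·√(0.8·0.2/135) = 1.96·0.0344 = 6.7 points.

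**Clustered half-width.** The design effect is DEFF = 1 + (m − 1)·ICC, with m = 135 / number of surgeons, and the effective number of ratings is 135/DEFF. With 12 surgeons m = 11.25, and t with 11 df is 2.201. The half-width is 2.201·0.0344·√DEFF. The coverage columns come from beta-binomial simulation of the exact 95% interval. The SAP does not say which interval method it will use for proportions.

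| ICC | DEFF, 12 surgeons | Effective ratings | Half-width, t 11 df (points) | Coverage, 12 surgeons | Coverage, 40 surgeons |
|---|---|---|---|---|---|
| 0.01 | 1.10 | 122 | 8.0 | 95% | 96% |
| 0.05 | 1.51 | 89 | 9.3 | 90% | 95% |
| 0.1 | 2.03 | 67 | 10.8 | 85% | 93% |
| 0.3 | 4.08 | 33 | 15.3 | 69% | 88% |

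Part of the widening comes from the degrees of freedom alone: with no correlation at all, 2.201·0.0344 = 7.6 points. Coverage can slightly exceed 95% because the exact interval is conservative.

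**Sensitivity.**
- Fewer raters make it worse. With 10 surgeons, the SAP 7.3 maximum at one per site, coverage is 83% at ICC 0.1 and 65% at ICC 0.3.
- Uneven recruitment also makes it worse. Four sites at the cap of 25 and seven with 5 each gives 135 ratings. The size-weighted cluster size is (4·25² + 7·5²)/135 = 19.8. With one surgeon per site, DEFF at ICC 0.1 is 1 + 18.8·0.1 = 2.88, so the interval should be √2.88 = 1.70 times as wide before any t correction. The even split over 12 gives √2.03 = 1.42.
- More raters make it milder. With 40 surgeons m = 3.375, and DEFF at ICC 0.1 is 1 + 2.375·0.1 = 1.24, a factor of 1.11.

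**The case against.** The strongest reply is that the rated unit is an implantation. The questionnaire concerns handling in that operation, and eight mesh sizes are available. The share of implantations rated satisfactory is then a legitimate descriptive summary on a set of subjects. This stands. A reader might infer that the plan uses the wrong unit of observation, but the documents do not support that. What is missing is a variance allowance for repeated raters, which matters when the interval is read as applying beyond the participating surgeons. The SAP does not say how the interval should be read.

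A reader might also infer that the interval is far too narrow and rests on a handful of surgeons. Neither is established. Only site counts are stated, a site may have more than one investigator, and no ICC is given. At ICC 0.01 coverage is nominal, and with 40 surgeons the shortfall is small up to ICC 0.1.

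Nor do the documents show that a surgeon identifier is ready to use. Protocol 17.2 gives registry accounts to surgeon members or designees, so an account need not identify the operator. Protocol 17.4 names only site and subject numbers as recorded identifiers.

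Reporting the endpoint on three sets is largely a matter of preference; the SAP does not claim that the repeats add information.

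Finally, the endpoint is descriptive and does not measure the stated secondary objective, which is safety. That limits the priority. It does not make an interval that ignores known repetition correct.

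**Conclusion.** The point holds in a limited form. Ratings will usually repeat within surgeons, the only interval specified ignores this, and any positive within-surgeon correlation makes it too narrow. The direction is clear but the size is not. Over the assumed range, true coverage of the nominal 95% interval runs from essentially nominal (ICC 0.01, or many surgeons with weak correlation) down to about 69% (12 surgeons, ICC 0.3), and lower with fewer raters or stronger correlation. These figures depend on the assumed 80% satisfied, a yes/no scale, an even spread of ratings and the chosen surgeon counts. No conclusion about hernia incidence or safety is affected, so this is a low-priority correction.

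**What to change.** In SAP 7.9, under surgeon satisfaction:

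- Report the number of implanting surgeons and the distribution of ratings per surgeon.
- Compute the 95% CI with the surgeon as cluster, either by a cluster-robust variance with surgeons minus 1 degrees of freedom or from surgeon-level means. If the registry extract carries no operator identifier, use the site as cluster, with sites minus 1 degrees of freedom.
- Alternatively, give the frequencies or means without a CI and say that they describe the implantations in this study only.

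Reconcile the site count at the same time (6 to 10 in SAP 7.3; up to 12 in SAP section 5 and the protocol), since it bounds the number of clusters if site is used.

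The cost is a short SAP amendment, a different procedure, a check of whether the extract identifies the operator, and a wider reported interval. If site serves as the fallback cluster, no new data collection is needed.
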